#### Cardiovascular events and mortality:

The cardiovascular event rates and mortality data will be monitored after participant recruitment. The admissions, cardiovascular event rates and mortality data will be retrieved from the Clinical Management System by the research nurse, who will also ascertain any admissions to private hospitals. The same information will too be collected via patient's or family member's self-report.

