#### Randomization and blinding

After collecting baseline data, the research nurse will randomly allocate patients into the intervention or control group. Block randomization (block size: 8, 10, or 12) will be used to ensure even participant distribution between the two groups. The block size and respective study group allocation sequence will be determined using a computer-generated sequence. Chronologically recruited patients will be allocated to the study groups by the nurse according to this computer-generated sequence. Participants allocated to the intervention group will receive the i-CARE intervention, while those allocated to the control group will continue to receive conventional care as arranged by the hospital. An independent research assistant who is blinded to study group allocations will collect post-intervention data.

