#### Intervention group: i-CARE

Participants in the intervention group will receive a 12-week i-CARE intervention, which will be designed to cover the core elements of CAD self-care: self-care maintenance, self-care monitoring and self-care management. The intervention will comprise: 1) a single individualized face-to-face session and 2) an internet-based intervention through a mobile application, which is developed by the investigation team of this project. Various behavior change techniques will be used to increase the self-efficacy of CAD patients in enacting self-care behaviors. The details of these two care components are described as follow.

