##### 1) Face-to-face orientation session

This single face-to-face session serves to orientate and prepare participants to actively engage in the upcoming internet-based intervention. The research nurse (RA1) will highlight the crucial role of patients themselves in managing the disease by assisting them to understand the links between their self-care behaviors and health consequences. A subsequent interactive skill-building session to ensure patients acquire the skills required for performing self-monitoring techniques, including blood pressure, heart rate and blood glucose measurement. The participants will be required to perform return demonstration to ensure skill acquisition. The nurse will then introduce the mobile application and assist the participants to register an account. Upon successful registration, a password will be provided. He/she will demonstrate the key functions of the application and assist the participant to personalize the setting according to their individualized risk profile and preferences. The nurse will emphasize the importance of compliance to self-care behaviors and will facilitate the participants to set self-directed goals at the end of this session.

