The chat room will serve as a platform to facilitate the nurse to provide coaching to motivate and facilitate behavioral changes of the participants. The nurse will review the self-monitoring data and keep track on the progress of goal attainment of each participant. He/she will initiate chatting with the participants in this platform weekly, to identify any problems that the participants encountered in their daily practice of self-care behaviors, and will explore the underlying barriers, then advise resolving methods to minimize the barriers and improve adherence. Health counselling and advice given will be documented to guide subsequent communication. Throughout the process, the nurse will adopt therapeutic communication skills, and a supportive and non-judgmental attitude. The participants can also initiate the communication with the nurse in the chat room regarding disease management. The nurse will offer advice and counselling accordingly during office hours. An automatic system-generated message will pop up to remind the participants to seek urgent medical care for newly onset symptoms that may suggestive of disease exacerbation or deterioration.

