#### Fidelity monitoring of the study intervention

To optimize fidelity of the study intervention, a training manual will be used to guide the intervention delivery. The research nurse (RA1) will receive two weeks of comprehensive training from the investigation team on CAD, principles and skills in patient education, methods to deliver the study protocol and counselling via the chatroom. For fidelity monitoring, the principal investigator will randomly select 10% of the face-to-face educative sessions for fidelity monitoring. The educative sessions will be audiotaped with the participants' consent, the chat record between the research nurse and participants in the chatroom will be reviewed. Thirdly, the login activities, number of completed sessions, the self-monitoring dashboard activities of all participants will be tracked. All of these data will be used to interpret the RCT findings.

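### Cardiovascular events and admissions are ascertained by the unblinded nurse who delivers i-CARE, so private-hospital and self-reported events are liable to be captured unequally between arms

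*Combined protocol and SAP*

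**What the plan says.** The combined protocol and SAP deals with event collection in three places.

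- **Cardiovascular events and mortality** (secondary outcomes): admissions, events and deaths are "retrieved from the Clinical Management System by the research nurse, who will also ascertain any admissions to private hospitals". It adds "The same information will too be collected via" report by the patient or a family member. No collector, form or timetable is named for that second route.
- **Randomization and blinding**: "An independent research assistant who is blinded to study group allocations will collect post-intervention data". The same section says "the research nurse will randomly allocate patients into the intervention or control group".
- **Data collection procedure**: the assistant without knowledge of allocation is given the physiological, anthropometric and biomarker measurements. Events, admissions and deaths are not on that list.

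The research nurse's other duties are these:

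- Orientation session: "The research nurse (RA1) will highlight the crucial role of patients themselves in managing the disease".
- Fidelity monitoring: "The research nurse (RA1) will receive two weeks of comprehensive training from the investigation team", and that training includes counselling through the chat room.
- Chat room, under the internet-based intervention: "He/she will initiate chatting with the participants in this platform weekly".
- Duration: "Participants in the intervention group will receive a 12-week i-CARE intervention".

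Control group: Usual care describes hospital care only, with no scheduled contact with the nurse.

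**The concern.** Study design calls the trial single-blinded, and Randomization and blinding reads as if all post-intervention data were collected blind. Event data are not: the section that defines the outcome gives them to someone who knows the allocation and delivers the intervention.

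The routes to an event differ in how far they depend on contact. A Clinical Management System search finds the same records whoever the patient has been talking to. A private-hospital admission, or an event known only from the patient or family, comes to light when somebody asks or is told. The nurse has about 12 scheduled conversations with each intervention participant and none described with controls. The two arms may therefore be observed with different intensity on exactly those routes.

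At stake is the between-arm comparison of events and admissions. Fuller capture in the intervention arm would work against i-CARE, by hiding a benefit or suggesting harm. Knowledge of allocation could also act in the other direction. The planned GEE analysis cannot recover events that were never recorded.

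**Working it through.** **Step 1. Who collects what.**

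| Item | Person | Section |
|---|---|---|
| Post-intervention data, in general | Blinded assistant | Randomization and blinding |
| Physiological, anthropometric, biomarker data | Blinded assistant | Data collection procedure |
| Events, admissions, deaths; private-hospital admissions | Research nurse | Cardiovascular events and mortality |
| Patient or family report of the same | Not stated | Cardiovascular events and mortality |
| Allocation | Research nurse | Randomization and blinding; Data collection procedure |
| Orientation session | Research nurse (RA1) | Face-to-face orientation session |
| Weekly chat, intervention arm | Nurse; RA1 is trained for it | Internet-based intervention; Fidelity monitoring |

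The events section does not repeat the label RA1, but only one research nurse role is described. The general sentence on blinded collection does not settle the matter: the specific text on events names the nurse, and the specific text on the assistant leaves events out.

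**Step 2. The plan's own figures.** No event rate, private-hospital share or event-based power is given, so there is no stated event figure to reproduce. The group size used below does reproduce: 100/(1 − 0.25) = 133.3, rounded up to 134 per group, 268 in total. It is set by the primary outcome and this point does not change it.

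**Step 3. Illustration of size. All inputs are assumed.** Let *s* be the share of events visible only through private-hospital or self-report routes, with capture of those events c_I in the intervention arm and c_C in control. Let the true risks be equal and the remaining events be fully captured in both arms. Then

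recorded ratio = [(1 − s) + s·c_I] / [(1 − s) + s·c_C].

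With c_I = 0.95 and c_C = 0.60:

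- s = 0.10: 0.995/0.960 = 1.036
- s = 0.20: 0.990/0.920 = 1.076
- s = 0.30: 0.985/0.880 = 1.119

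With c_I = 0.95 and a wider range for the rest:

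| s | c_C = 0.80 | c_C = 0.50 |
|---|---|---|
| 0.10 | 1.015 | 1.047 |
| 0.30 | 1.048 | 1.159 |
| 0.50 | 1.083 | 1.300 |

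As s approaches 0, the ratio approaches 1 whatever the capture rates. These ratios hold the gap constant throughout follow-up; because the weekly contact ends at 12 weeks, the effect over 6 months would be diluted.

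**Step 4. Against sampling error.** For 134 per arm and an assumed true risk of 10%, the standard error of the log risk ratio is √[2 × 0.90/(134 × 0.10)] = 0.367. The 95% range around a true ratio of 1 is exp(±1.96 × 0.367), or 0.49 to 2.05.

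The two-sided false-positive rate is Φ[(d − 1.96·SE0)/SE1] + Φ[(−d − 1.96·SE0)/SE1], where d is the spurious risk difference and SE0 and SE1 are its pooled and unpooled standard errors. For 10% risk, s = 0.30 and capture of 95% against 50%, the recorded risks are 9.85% and 8.50%, so d = 0.0135. SE0 and SE1 are both about 0.0353, and the rate is 0.057 + 0.010 = 6.7%. Over risks of 5% to 20% and the grid above it runs from about 5.0% to 16.4%.

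**The case against.** The strongest reply is that the events section describes one procedure without distinction by arm: a record search, an enquiry about private admissions, and self-report. Nothing says that chat is a source of events; its stated purposes are coaching, goal progress and barriers to self-care. This stands as far as it goes. A reader might infer that events will be captured more fully in the intervention arm, but the documents do not support that certainty, because they give no schedule for asking either arm. Liable to be is as far as the text allows.

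It is also fair that the Clinical Management System search does not depend on contact, that death leaves little room for recall or judgement, that the extra contact lasts 12 weeks, and that the illustrative ratios are small beside sampling error in a trial of this size. Events are one secondary outcome, absent from the two stated aims.

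Two further inferences go too far:

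- **The app's urgent-care message biases the event count.** The message is part of i-CARE. Under intention-to-treat, admissions that follow from it are an effect of the intervention, not an error of ascertainment.
- **The nurse adjudicates events.** The text says that data are retrieved and private admissions ascertained. No adjudication role is assigned.

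None of this answers the core point. The person collecting events is unblinded, her or his scheduled contact is one-sided, and three sections disagree on what is collected blind.

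**Conclusion.** The point holds in a limited form. As written, the single-blinding does not extend to cardiovascular events, admissions and mortality. Private-hospital and self-reported events are open to unequal capture, most plausibly in favour of fuller recording in the intervention arm during the first 12 weeks. Clinical Management System events and deaths are much less exposed. The primary outcome and the sample size are unaffected.

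The size of the bias cannot be derived from the documents. A recorded ratio of about 1.04 to 1.12 under no true difference rests wholly on the assumptions that 10% to 30% of events lie outside the Clinical Management System and that capture of those is 95% against 60%. If nearly all events are in that system, the bias is negligible. The direction is a judgement too, since unblinded collection could also act the other way.

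The change is worth making because it is cheap and because missed events cannot be recovered at analysis.

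**What to change.** Reconcile Randomization and blinding, Cardiovascular events and mortality, and Data collection procedure as follows.

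1. Assign ascertainment of events, admissions and mortality to the blinded research assistant already in the plan.
2. Use the same Clinical Management System search and the same scripted question on private-hospital admissions for both arms at 3 and 6 months. Reach those who miss a visit by telephone or through a family member.
3. Count an event first learned through chat in the between-arm comparison only if this common procedure also finds it.
4. Add a sensitivity analysis restricted to Clinical Management System events.
5. Ask the event questions after the physical measurements, so that an answer revealing the allocation cannot influence them.

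The outcome itself need not be narrowed; admissions can stay as listed.

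**Cost.** Protocol wording, Clinical Management System access for the assistant, a few more minutes per contact, and follow-up calls for missed visits. A few events known only from chat will leave the comparison.

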## **Data collection procedure**

After obtaining the approval from the respective ethics research committees, the research nurse will recruit eligible participants from the cardiac clinics and wards of two regional hospitals in Hong Kong. The local PI will identify potential subjects from the admission record and follow-up list of the cardiac ward and clinics respectively, and refer them to the research nurse. The research nurse will screen their eligibility according to the predefined criteria. All the eligible patients will be invited to participate. He/she will introduce the study to potential participants verbally, supplemented with a written information sheet. After obtaining the participants'

written informed consent, the nurse will collect socio-demographic and clinical data through patient's self-report and medical record review, while the nurse will assist participants to complete the SC-CHDI, SAQ and MacNew through a secured online platform Qualtrics. The physiological, anthropometric and biomarkers will be collected according to the standard protocol. The research nurse will then allocate the participants into intervention or control group by block randomization, to receive the i-CARE intervention or usual care, respectively. The post-intervention data will be collected through the mobile application, a message will be popped up to remind the participants at 3 and 6 months thereafter. A trained research assistant who has no knowledge of the group allocation, will be responsible for collecting the post-intervention physiological, anthropometric and biomarkers. A subsample of the participants will be invited to participate in the qualitative phase. Semi-structured interviews will be conducted by the principal investigator with an interview guide, which includes open-ended questions to enquire about their engagement experience in the intervention.

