**Background**

Cardiovascular diseases (CVD), the leading cause of death globally, remains a significant and ever-growing public health concern in every region of the world. Advancements in CVD diagnosis and treatments and increasing life expectancy have resulted in high prevalence of patients living with CVD, who are at high risk of morbidity and mortality. The majority of CVD deaths are attributed to an acute manifestation of coronary artery disease (CAD), defined as narrowing of coronary arteries that causes insufficient myocardial blood flow due to accumulation of atherosclerotic plaque. CAD has reached an unequivocal pandemic status globally and locally, imposing not only significant physical and psychosocial burdens on patients, but also enormous service demands on the healthcare systems. Recent local statistics reported that CAD was responsible for 34,000 hospital admissions per year (i.e., 93 admissions per day). Moreover, a cost-of-illness analysis revealed the mean first-year total direct medical expenditure associated with a newly diagnosed stable CAD patient in Hong Kong was up to US\$11,477. This substantial disease burden on healthcare is expected to increase further with inevitable trend of ageing population and increasing life expectancy.

In response to changes in the epidemiology of CAD, existing care efforts are directed towards the provision of emergency services to patients during acute disease manifestations (i.e. acute myocardial infarction) and cardiac rehabilitation following revascularization procedures. There is a lack of proactive care for patients with mild to moderate CAD who have not yet developed an acute exacerbation, representing a major service gap, or “missing piece”. These patients account for two thirds of all acute myocardial infarction, despite having coronary artery stenosis levels of <50%. In addition, an episodic, acute care remains a major focus of our healthcare system, whereas secondary prevention of CAD cultivated by effective risk factor management and self-care receive inadequate attention. Therefore, it is crucial to fill this “missing piece” in the CAD management continuum in order to reduce morbidity and mortality in patients with established CAD.

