### Study participants

Adults will be eligible to join the study if they are: 1) living in the community, 2) owning a smartphone with internet access, 3) communicable in Cantonese, 4) able to type in Chinese or English, and 5) with a confirmed diagnosis of CAD. Individuals will be excluded if they have: 1) enrolled to a structured center-based or home-based cardiac rehabilitation programme in the past year, 2) known psychiatric problems, 3) impaired cognitive functioning (i.e. Abbreviated Mental Test  $\leq 6$ ), and 4) terminal disease with life expectancy  $< 1$  year.

For the RCT, the sample size is determined on the basis of a systematic review that identified small to medium effect sizes (0.42–0.66) of information and communication technology-based cardiac rehabilitation on health behaviors among patients with CAD. This study will conservatively assume an effect size as 0.4. The power analysis software PASS 14 (NCSS, Kaysville, UT) estimated that a sample size of 100 subjects per study group would give the proposed two-arm randomized controlled trial 80% power at a two-sided 5% level of significance to detect an effect size of 0.4 on the primary outcome between the control and intervention groups at the post-intervention time point. After allowing for a potential dropout rate of up to 25%, 268 subjects (i.e. 134/group). For the qualitative phase, a criterion sampling of 30 participants who have received the i-CARE program will be invited to join on the basis of their post-intervention changes in the primary outcome, with 10 participants from each

category (low, medium and high percentile). Maximum variations in the participants' sociodemographic and clinical characteristics will also be considered in the sampling procedure to ensure a wider range of data.

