### **Data Analysis**

For the RCT study, data analysis will be performed according to the intention-to-treat principle. Baseline characteristics between the two study arms will be compared by t-test, chi-square or Fisher's exact test as appropriate. The generalized estimating equation (GEE) model will be used to compare the differential changes on the outcomes across the time points T0, T1 and T2 between the two study arms with adjustment for potential confounding variables. Baseline characteristics with p values < 0.25 for between-group difference will be considered as potential confounding variables. GEE model can account for intra-correlated repeated measures data and accommodate missing data caused by incomplete assessments or dropout, provided that the data are missed at random, and thus are particularly suitable for intention-to-treat analysis without the need of imputation for missing data. All statistical analyses will be performed using IBM SPSS 25.0. All statistical tests will be two-sided and a p-value < 0.05 will be considered statistically significant. For the qualitative study, the audio-taped data will be transcribed verbatim. The principal investigator will ensure accuracy of the transcription by cross-checking. Content analysis will be adopted to code the qualitative data on participants' perceptions and acceptability of the technology-based self-care support intervention. The analysis will also seek to understand why and how the study intervention influences patients' health behaviors. The codes will be organized into categories and subcategories, which will be analyzed for emerging themes. The trustworthiness of the qualitative analysis will be enhanced by audio-taping of the interviews, conducting an audit trail, involving two team members to code the qualitative data independently.

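### Ward and clinic patients are pooled in a change-from-baseline GEE with no setting-by-time term; if the two settings change differently from T0, precision is lost that the planned p<0.25 covariate rule cannot recover

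*Combined protocol and SAP*

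**What the plan says.** All references are to the combined protocol and SAP.

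- **Recruitment.** Under Data collection procedure, "the research nurse will recruit eligible participants from the cardiac clinics and wards of two regional hospitals in Hong Kong". The local investigator is to "identify potential subjects from the admission record and follow-up list of the cardiac ward and clinics respectively", so ward patients are found through an admission and clinic patients through routine follow-up.
- **Eligibility.** Study participants begins: "Adults will be eligible to join the study if they are: 1) living in the community". The listed criteria include nothing on clinical stability or time since admission.
- **Timing of T0.** Randomization and blinding states: "After collecting baseline data, the research nurse will randomly allocate patients into the intervention or control group". T0 therefore precedes allocation, but its interval from admission or discharge is not given.
- **Randomisation.** Permuted blocks of 8, 10 or 12. No stratification by setting is stated.
- **Analysis.** The GEE is to "compare the differential changes on the outcomes across the time points T0, T1 and T2 between the two study arms with adjustment" for potential confounders, and the rule for choosing them is: "Baseline characteristics with p values < 0.25 for between-group difference will be considered as potential confounding variables". Neither recruitment setting nor a setting-by-time term is mentioned.
- **Sample size.** Study participants gives 100 per group for 80% power at a two-sided 5% level and an effect size of 0.4. The comparison is between groups at the post-intervention time point. Allowing for 25% dropout gives 134 per group, 268 in all. No SD, correlation or ward share is given.

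**The concern.** The planned contrast is change from T0. A ward patient assessed close to an admission may start from a disturbed baseline and be followed up in the community, so the T0-to-T1 change could include some recovery whichever arm the patient is in. A clinic patient's change would contain less of it, or none. Pooling the two groups without modelling the difference puts a between-setting component into the residual variance of change.

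The plan has an adjustment rule, but it does not address this. Under randomisation, setting would pass a p<0.25 screen in only about one trial in four. If it passed, it would ordinarily enter as a main effect, which shifts all of a participant's visits equally and so says nothing about change.

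What is at stake is precision, for the primary outcome and for the secondary outcomes analysed by the same GEE. Functional status and blood pressure may be more exposed to a recent admission than self-reported self-care behaviour, but the documents do not show this either way.

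**Working it through.** **1. The plan's own figure.** For a standardised difference of 0.4 at two-sided 5%, the normal approximation gives 99 per arm. With 100 per arm, power is 80.7% by that approximation and 80.4% by the noncentral t. Dropout: 100/0.75 = 133.3, rounded up to 134 per arm, 268 in total. The stated sample size reproduces.

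**2. Variance of change.** Let p be the ward share, d the extra T0-to-T1 change of ward patients in both arms (in within-setting outcome SDs), and r the within-setting T0-T1 correlation, with equal SDs at both visits. Within an arm:

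- variance of change if setting-by-time is modelled: 2(1-r)
- variance of change if it is not: 2(1-r) + p(1-p)d²
- inflation F = 1 + p(1-p)d² / [2(1-r)]

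**3. Power for the change contrast.** None of p, d and r is in the documents. I assume p = 0.3 to 0.5, r = 0.3 to 0.7, 100 per arm, and an effect of 0.4 within-setting change SD (80.4% power with no recovery difference). The effective standardised effect is 0.4/√F.

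| d | Least inflation (p=0.3, r=0.3) | Power | Most inflation (p=0.5, r=0.7) | Power | Loss, points |
|---|---|---|---|---|---|
| 0.3 | F=1.014 | 79.8% | F=1.038 | 78.9% | 0.5 to 1.5 |
| 0.5 | F=1.038 | 78.9% | F=1.104 | 76.4% | 1.5 to 4.0 |
| 1.0 | F=1.150 | 74.7% | F=1.417 | 65.7% | 5.7 to 14.6 |

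For example, at d=1.0, p=0.5, r=0.7: F = 1 + 0.25 × 1 / 0.6 = 1.417, and 0.4/√1.417 = 0.336.

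**4. Why a main effect does not help.** A setting main effect adds the same constant to a participant's fitted value at T0, T1 and T2. It cancels in T1 minus T0, so with complete data the group-by-time estimate is unchanged. Only setting-by-time absorbs a difference in change.

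**5. Simulation check.** GEE with independence working correlation and robust standard errors, 200 patients, 3,000 runs, r=0.5, p=0.5, true effect 0.40 outcome SD (at r=0.5 the change SD equals the outcome SD):

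| d | Power, no setting term | Power, main effect only | Power, setting-by-time |
|---|---|---|---|
| 0 | 79.6% | 79.6% | 79.8% |
| 0.5 | 77.7% | 77.7% | 80.2% |
| 0.8 | 75.3% | 75.3% | 81.8% |
| 1.0 | 71.5% | 71.5% | 80.5% |

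The mean estimate was about 0.40 in every row. With no true effect and d=0.8, type I error was 6.0% without the term and 5.7% with it. The added noise costs power; it does not bias the estimate or disturb the test. When recovery does not differ (d=0), the term costs nothing visible.

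**6. Sensitivity to the meaning of 0.4.** If 0.4 is read in outcome SDs, change-score power with 100 per arm and p=0.5 is:

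- r=0.7: 95% with no recovery difference, 86% at d=1.0
- r=0.3: 66% with no recovery difference, 59% at d=1.0

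If 0.4 is already standardised on the pooled change SD, the setting noise is inside it. Power stays at 80.7% (normal approximation), and the term raises it to 83.2% at d=0.5, p=0.5, because the residual variance falls to 1 - 0.25 × 0.25 = 0.9375.

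**The case against.** The case against is substantial, and most of it limits the size of the point.

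- **Every driver is assumed.** Ward share, correlation and recovery difference are absent from the documents, and so is the interval between admission and T0. Nothing shows that self-care behaviour, the primary outcome, recovers after an admission. This stands: recovery is a possibility to guard against, not an established fact.
- **A reader might infer that the stated 80% power is wrong or the trial too small.** The documents do not support that. The figure is for the between-group difference at the post-intervention time point, which a disturbed T0 does not affect, and it reproduces.
- **A reader might quote the 66% corner as the expected power.** It needs a 1.0 SD recovery difference, 50% ward patients, correlation 0.7, and 0.4 read in change SDs. That reading makes the true effect only 0.4 × √0.6 = 0.31 outcome SD. With 0.4 outcome SD the same corner gives 86%.
- **There is some margin.** The 25% dropout is an upper allowance. With all 134 per arm retained, planned power is 90%; at r=0.5, p=0.5, d=1.0 the change contrast would still have 83%.
- **A reader might infer bias, or a second harm from chance imbalance in ward share.** Randomisation precludes systematic bias. With 134 per arm, the 95% range for a chance difference in ward share is 1.96 × √(2p(1-p)/134), or 11 to 12 percentage points. That is the same variance seen in a single trial, and the standard error already covers it.
- **The same argument could be made for hospital or any other predictor of change.** That is true, so this is an efficiency choice. Setting is a natural candidate because the two recruitment routes differ in how closely T0 may follow an admission.

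What remains is that the plan pools the settings, analyses change, and has a covariate rule that cannot remove a setting difference in change.

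**Conclusion.** The point holds as a conditional loss of precision. If ward and clinic patients change differently from T0, the planned GEE carries avoidable variance in the group-by-time contrast, and the p<0.25 rule cannot remove it. Under the assumptions in step 3 of the working, the loss is about 0.5 to 1.5 power points at a 0.3 SD recovery difference and 1.5 to 4 points at 0.5 SD. It becomes large, about 6 to 15 points, only at an extreme 1.0 SD. With no difference in recovery there is no loss.

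The size depends on unstated inputs and on how the effect size of 0.4 is standardised. The finding does not show bias, an inflated type I error or an error in the sample size. It is worth acting on because the remedy costs almost nothing and is most credible if fixed before data are seen.

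**What to change.** Record recruitment setting (ward or clinic) as a baseline variable for each participant. In the Data Analysis section, prespecify setting and setting-by-time as fixed terms in every GEE outcome model, whatever the baseline p-value, and do not leave setting to the p<0.25 screen.

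The cost is one data field already known at recruitment, a sentence of analysis text, and three model parameters (one for setting, two for setting by T1 and T2) in a model with about 200 or more participants. The sample size does not change.
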